#### **9.4.2 Immunogenicity Endpoints**

A description of immunogenicity assessments is contained in Section 8.2.

The immune responses will be measured for each of the following serotypes contained in V114: 1, 3, 4, 5, 6A, 6B, 7F, 9V, 14, 18C, 19A, 19F, 22F, 23F, and 33F. The primary immunogenicity endpoints include:

- Proportion of participants with anti-PnPs serotype-specific IgG  $\geq 0.35$   $\mu$ g/mL at 30 days PD3.

- Anti-PnPs serotype-specific IgG GMCs at 30 days PD3.

The secondary immunogenicity analysis endpoints include:

- Anti-PnPs serotype-specific IgG GMCs at 30 days PD4.

## 9.5 Analysis Populations

### 9.5.1 Immunogenicity Analysis Populations

The PP population will serve as the primary population for the analysis of immunogenicity data in this study. The PP population consists of all randomized participants without deviations from the protocol that may substantially affect the results of the immunogenicity endpoint(s). Potential deviations that may result in the exclusion of a participant from the PP population for all immunogenicity analyses include:

- Failure to receive primary infant series vaccination (V114 Doses 1, 2, and 3) as per vaccination schedule
- Receipt of prohibited medication or prohibited vaccine before study vaccination

Additional potential deviations that may result in the exclusion from the PP immunogenicity analyses at a particular time point include:

- Failure to receive Dose 4 of V114 according to vaccination schedule required at the time point for the analysis
- Failure to receive the scheduled doses of V114 with the specified intervals/time window (at least 28 days between Doses 1 and 2 and between Doses 2 and 3 [for PD3 analysis], 12 months to 1 day before 16 months of age for Dose 4 [for PD4 analyses])
- Receipt of prohibited medication or prohibited vaccine before a blood sample collection
- Collection of blood sample at the time point for the analysis outside the prespecified window (as described in Section 1.3)

The final determination on protocol deviations, and thereby the composition of the PP population, will be made before the final database lock.

A supportive analysis using the FAS population may also be performed for the primary immunogenicity endpoints. The FAS population consists of all randomized participants who received at least 1 study vaccination and have at least 1 serology result.

### 9.5.2 Safety Analysis Populations

Safety analyses will be conducted in the APaT population, which consists of all randomized participants who received at least one dose of study vaccination.

At least 1 temperature measurement obtained after study intervention is required for inclusion in the analysis of temperature.

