Nonstudy Pediatric Vaccines	(X)	(X)	(X)		(X)		Sponsor will not provide nonstudy pediatric vaccines, but they are permitted to be given during the study. If given at the same time, oral vaccines are recommended to be given before the study vaccine and other injectable vaccines. Other injectable vaccines are administered after the study vaccine and in a separate limb.  See Section 6.5 for details on concomitant vaccines.
Provide Paper VRC	X	X	X		X		A paper VRC will be provided to record AEs, body temperature, concomitant medications, and nonstudy vaccinations. Instructions for using the paper VRC will be reviewed with the participant's parent or legally acceptable representative.  See Section 8.1.9 and 8.3.3 for details regarding the completion of the paper VRC.
Collect Paper VRC and Review VRC data with Participant's Parent or Legally Acceptable Representative		X	X	X		X	See Section 8.1.9 for details.
Safety Procedures							
Complete Physical Examination	X						To be performed by the investigator or medically qualified designee before vaccine is administered (see Section 8.3.1).
Targeted Physical Examination		X	X		X		To be performed by the investigator or medically qualified designee before vaccine is administered (see Section 8.3.1).
Body Temperature Measurement	X	X	X		X		Each participant's body temperature must be taken before vaccination (see Section 8.3.2 for method). Participants who have febrile illness at or within 72 hours of vaccination must be rescheduled.

Study Period:	Intervention						Comments
Visit Number	1	2	3	4	5	6	
Scheduled Time:	Age: ~2 months (Dose 1)	Age: ~4 months (Dose 2)	Age: ~6 months (Dose 3)	~1 month after Dose 3	Age: ~12 to 15 months (Dose 4)	~1 month after Dose 4	Months of age is calculated according to the participant's birth date
Visit Window a	≥42 days of age to ≤90 days of age	4 months of age to 1 day before 5 months of age	6 months of age to 1 day before 7 months of age	Day 28 to Day 42 Postdose 3	12 months of age to 1 day before 16 months of age	Day 28 to Day 42 Postdose 4	
15-Minute Postvaccination Observation Period	X	X	X		X		The observation period can be extended if clinically indicated.
AE Monitoring	X	X	X	X	X	X	Nonserious AEs are to be reported from Days 1 through 14 after each vaccination. SAEs and deaths are to be reported throughout the duration of an individual's study participation.

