## **7.2 Participant Withdrawal From the Study**

A participant must be withdrawn from the study if the participant's legally acceptable representative withdraws consent from the study.

If a participant withdraws from the study, they will no longer receive study intervention or be followed at scheduled protocol visits.

Specific details regarding procedures to be performed at the time of withdrawal from the study, as well as specific details regarding withdrawal from future biomedical research, are outlined in Section 8.1.10. The procedures to be performed should a participant repeatedly fail to return for scheduled visits and/or if the study site is unable to contact the participant are outlined in Section 7.3.

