## **7.3 Lost to Follow-up**

If a participant fails to return to the clinic for a required study visit and/or if the site is unable to contact the participant, the following procedures are to be performed:

- The site must attempt to contact the participant's legally acceptable representative and reschedule the missed visit. If the participant's legally acceptable representative is

contacted, the participant's legally acceptable representative should be counseled on the importance of maintaining the protocol-specified visit schedule.

- The investigator or designee must make every effort to regain contact with the participant's legally acceptable representative at each missed visit (eg, telephone calls and/or a certified letter to the participant's legally acceptable representative last known mailing address or locally equivalent methods). These contact attempts should be documented in the participant's medical record.
- Note: A participant is not considered lost to follow-up until the last scheduled visit for the individual participant. The missing data for the participant will be managed via the prespecified statistical data handling and analysis guidelines.

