### **8.1.9 Vaccination Report Card**

The investigator or delegate will train the participant's parent or legally acceptable representative in the use of the paper VRC as indicated in Section 1.3.

After providing paper VRC, contact the participant's parent or legally acceptable representative at least once at approximately Day 3 poststudy vaccination, to ensure timely completion of paper VRC during Day 1 to Day 7 for solicited injection-site AEs, solicited systemic AEs and temperature. The main purpose of the contact is to ensure the participant's legally acceptable representative records on the paper VRC and to answer any questions related to VRC. While these contacts are not for collection of AEs, if any potential SAE information is reported it should be reviewed during the contact.

The investigator or delegate will review the data captured on the paper VRC with the participant's parent or legally acceptable representative as indicated in Section 1.3. For the AEs outlined above, the investigator will use the information provided by the participant's parent or legally acceptable representative on the paper VRC, and verbally at the time of VRC review, to apply the appropriate assessment of intensity as described in Appendix 3.

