#### **9.4.1 Safety Endpoints**

Safety and tolerability will be assessed by clinical review of all relevant parameters including AEs and postvaccination temperature measurements after any vaccination with V114.

The safety endpoints include:

- Proportion of participants with solicited injection-site AEs (swelling, redness/erythema, tenderness/pain, and hard lump/induration) from Day 1 through Day 7 after any vaccination with V114
- Proportion of participants with solicited systemic AEs (irritability, drowsiness/somnolence, hives or welts/urticaria, and appetite loss/decreased appetite) from Day 1 through Day 7 after any vaccination with V114
- Proportions of participants with the broad AE categories consisting of any AE and a vaccine-related AE from Day 1 through Day 7 after any vaccination with V114
- Proportions of participants with an SAE, a vaccine-related SAE, and discontinuation due to an AE, and death from Day 1 through completion of study participation
- Participants body temperature measured from Day 1 through Day 7 after any vaccination with V114

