### 9.6.1 Statistical Methods for Immunogenicity Analyses

This section describes the statistical methods that address the primary and secondary immunogenicity objectives.

Immunogenicity analyses will be conducted for each of the 15 pneumococcal serotypes in V114 separately. To address the primary immunogenicity objectives, evaluation of the IgG response rates and GMCs at 30 days after the third dose of V114 will include descriptive summaries and 95% CIs. For IgG response rates, the CIs will be calculated based on the exact binomial method proposed by Clopper and Pearson [CLOPPER, C. J. and PEARSON, E. S. 1934]. For IgG GMCs, point estimates will be calculated by exponentiating the estimates of the mean of the natural log values. The CIs will be derived by exponentiating the CIs of the mean of the natural log values based on the t-distribution.

To address the secondary immunogenicity objective, evaluation of the IgG GMCs at 30 days after the fourth dose of V114 will include descriptive summaries and 95% CIs.

The primary and secondary endpoints may be summarized separately as soon as complete data for the specified time points become available.

A detailed analysis strategy for immunogenicity endpoints is listed in [Table 3](#).

Table 3 Analysis Strategy for Key Immunogenicity Variables

Endpoint/Variable (Description, Time Point)	Primary vs. Supportive Approach †	Statistical Method	Analysis Population	Missing Data Approach
Primary Endpoints				
IgG response rates at 30 days PD3	P	Descriptive Statistics (estimate, 95% CI)	PP	Missing data will not be imputed
	S		FAS	
IgG GMCs at 30 days PD3	P	Descriptive Statistics (estimate, 95% CI)	PP	Missing data will not be imputed
	S		FAS	
Secondary Endpoint				
IgG GMCs at 30 days PD4	P	Descriptive Statistics (estimate, 95% CI)	PP	Missing data will not be imputed

† P=Primary approach; S=Supportive approach.  
CI = confidence interval; FAS = Full Analysis Set; GMC = geometric mean concentration;  
IgG = immunoglobulin G; PP = Per-Protocol.

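### Do the solicited-AE proportions need their own rule for infants with no diary data, and does the summary's reference to each dose need by-dose tables?

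*Combined protocol and SAP*

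**What the plan says.** Section 9.5.2 sets one population for safety: "Safety analyses will be conducted in the APaT population, which consists of all randomized participants who received at least one dose of study vaccination". The next sentence makes the only exception: "At least 1 temperature measurement obtained after study intervention is required for inclusion in the analysis of temperature".

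Solicited injection-site and systemic AEs are primary endpoints (Sections 3 and 9.1). Section 9.4.1 pools them over doses; the injection-site item ends "hard lump/induration) from Day 1 through Day 7 after any vaccination with V114". Section 9.6.2 reports them with exact Clopper-Pearson intervals. Table 4 has no dose dimension and no missing-data column. Table 3, for immunogenicity, does have such a column, and its entry is "Missing data will not be imputed".

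On missing visits, Section 7.3 says: "The missing data for the participant will be managed via the prespecified statistical data handling and analysis guidelines". Section 9 contains no separate rule of that kind for safety.

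On data capture, Section 8.3.3 has the parent record temperature and solicited AEs on the same card for Days 1 to 7, and has immediate reactions in the 15-minute observation entered on the eCRF. The Schedule of Activities row beginning "Collect Paper VRC and Review VRC data with" is marked at Visits 2, 3, 4 and 6. Section 8.1.9 adds a contact at about Day 3 to secure completion of the card.

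The summary in Section 9.1 says that Section 9.6.2 describes the safety strategy for each vaccination. The same summary names Sections 9.2 to 9.12 as the comprehensive plan.

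**The concern.** Two things look wrong.

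First, temperature and solicited AEs share a card and a seven-day window, yet only temperature needs an observation for inclusion. Taken literally, an infant whose card never comes back is counted as having had no reaction. That could happen. The visit windows put the first card collection 30 to 110 days after Dose 1, and Section 7.2 says: "If a participant withdraws from the study, they will no longer receive study intervention or be followed at scheduled protocol visits". The Day 3 contact does not fill the gap, because Section 8.1.9 says: "While these contacts are not for collection of AEs, if any potential SAE information is reported it should be reviewed during the contact". One programmer might keep all vaccinated infants in the denominator, and another might borrow the temperature rule. A primary safety proportion would then depend on that choice, and the literal reading understates it.

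Second, a reader of Section 9.1 would expect reactogenicity by dose in Section 9.6.2 and would not find it. Rates per dose and over any dose are different quantities. The any-dose rate rises with the number of doses received and cannot show whether reactions change across the four doses.

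**Working it through.** **Inputs.** From the documents: 45 infants, all assumed evaluable for safety (Section 9.9.2); 38 evaluable at 30 days after Dose 3 (Section 9.9.1); exact binomial intervals (Section 9.6.2). Assumed, because the documents do not give them: the true solicited-AE rate *p*, and the number *m* of infants with no solicited data after any dose.

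**The plan's own figures.** With n = 45, Section 9.9.2 reproduces:
- 1 − (1 − 0.035)^45 = 79.9% (stated 80%).
- 1 − (1 − 0.015)^45 = 49.3% (stated 50%).
- Upper limit for 0/45: 1 − 0.025^(1/45) = 7.87% (stated 7.9%).

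No stated figure is wrong.

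**Timing of the first card.** The shortest gap is 4 months of age (120 days) − 90 = 30 days. The longest is one day before 5 months (152 days) − 42 = 110 days. This shows late collection. It does not show lost data, since the card is filled in on Days 1 to 7.

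**Effect of the denominator.** If reporting is unrelated to reacting, the literal count falls short by *p* × *m*/45:

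| *p* | m = 0 | m = 1 | m = 2 | m = 5 |
|---|---|---|---|---|
| 30% | 0 | 0.7 | 1.3 | 3.3 |
| 50% | 0 | 1.1 | 2.2 | 5.6 |
| 80% | 0 | 1.8 | 3.6 | 8.9 |

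(percentage points)

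With exact 95% intervals:
- m = 1: 22/44 = 50.0% (34.6 to 65.4) against 22/45 = 48.9% (33.7 to 64.2).
- m = 5: 20/40 = 50.0% (33.8 to 66.2) against 20/45 = 44.4% (29.6 to 60.0).

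The half-width for 22/45 is (64.2 − 33.7)/2 = 15.3 points.

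**How plausible is m = 5?** It means 5/45 = 11% of infants with no solicited information after any dose. Section 9.9.1 allows 45 − 38 = 7 infants to be non-evaluable at 30 days after Dose 3 for all reasons, and Section 9.5.1 includes mistimed doses or samples and prohibited products among them. Five is therefore a stress case.

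**Partly missing cards.** Assume a 30% rate per dose and independent doses. The any-dose rate is 1 − 0.7^k, or 30.0%, 51.0%, 65.7% and 76.0% for k = 1 to 4. If five infants each lack one of four cards, the result is (40/45) × 76.0 + (5/45) × 65.7 = 74.9%, a drop of 1.1 points. The spread over *k* shows dependence on exposure, which an as-treated quantity is expected to have. It is not bias.

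**The alternative denominator.** Take m = 5 with 20 reactors among the 40 infants with data. If none of the five reacted, the true figure is 20/45 = 44.4%: the plan's count is exact and 20/40 is 5.6 points too high. If all five reacted, it is 25/45 = 55.6%, and both counts are too low. Parents of reacting infants may well return cards more often, which favours the first case. Neither denominator is better in every situation.

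**Each against any.** Set side by side, the summary row in Section 9.1 speaks of each vaccination, the endpoints in Section 9.4.1 say any vaccination, and Section 9.6.2 with Table 4 names no dose. The optional early summaries after Doses 3 and 4 concern when data are complete and are not rates by dose. The primary safety objective in Section 3 is the proportion of participants with AEs and asks for nothing by dose.

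**The case for a change.** The best case for a change is that these are primary endpoints, the plan writes data-availability rules elsewhere (temperature, the Full Analysis Set, Table 3), and the pointer in Section 7.3 leads to nothing for safety. Settling the denominator before database lock would cost one sentence. By-dose summaries would use data already collected.

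Part of this stands. The plan does not say outright that an absent report counts as no event, and Section 9.6.2 does not contain what Section 9.1 says it does. The safeguards (Day 3 contact, verbal report when the card is reviewed, final-visit activities encouraged at withdrawal under Section 8.1.10) reduce missing data but do not say how it is counted.

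The rest does not carry. One general rule followed by one named exception leaves the general rule in force for everything else, so a denominator is prespecified. Temperature also differs in kind: a maximum cannot be formed without a reading, whereas an AE proportion counts reported events. An inclusion rule built on the card or verbal report would discard a solicited reaction recorded on the eCRF during the 15-minute observation if the infant had no card. A rule of one day of follow-up after a dose has no clear meaning for an any-dose endpoint, and it would still count an infant with most days missing as event-free. By-dose tables would be informative, but they are an addition that the stated objective does not require.

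**Conclusion.** No change follows. On the denominator, the plan has a workable rule, and the alternative trades a possible understatement for a possible overstatement. The effect is zero if every infant has some solicited data and about 1 point in the plausible cases (one infant without data at a 50% rate, or five infants each missing one of four cards). It reaches 5.6 points only if 11% of infants supply nothing, still well inside an interval half-width of about 15 points. These sizes rest on assumed rates and assumed numbers of missing infants, and the partial-card figure also assumes independent doses. Analysts would ordinarily show how many infants contributed solicited data beside the population size, which is enough for a reader to judge.

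The reference to each vaccination in Section 9.1 is a clerical mismatch in a summary that yields to the detailed sections, where the endpoint is over any dose. Section 9.3 states that the study is for estimation, with no hypothesis tests, so no decision turns on either point.

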## 9.6 Statistical Methods

Statistical testing and inference for immunogenicity and safety analyses are described in Section 9.6.1 and Section 9.6.2, respectively. Section 9.6.3 describes how demographic and baseline characteristics will be summarized.

### 9.6.1 Statistical Methods for Immunogenicity Analyses

This section describes the statistical methods that address the primary and secondary immunogenicity objectives.

Immunogenicity analyses will be conducted for each of the 15 pneumococcal serotypes in V114 separately. To address the primary immunogenicity objectives, evaluation of the IgG response rates and GMCs at 30 days after the third dose of V114 will include descriptive summaries and 95% CIs. For IgG response rates, the CIs will be calculated based on the exact binomial method proposed by Clopper and Pearson [CLOPPER, C. J. and PEARSON, E. S. 1934]. For IgG GMCs, point estimates will be calculated by exponentiating the estimates of the mean of the natural log values. The CIs will be derived by exponentiating the CIs of the mean of the natural log values based on the t-distribution.

To address the secondary immunogenicity objective, evaluation of the IgG GMCs at 30 days after the fourth dose of V114 will include descriptive summaries and 95% CIs.

The primary and secondary endpoints may be summarized separately as soon as complete data for the specified time points become available.

A detailed analysis strategy for immunogenicity endpoints is listed in [Table 3](#).

Table 3 Analysis Strategy for Key Immunogenicity Variables

Endpoint/Variable (Description, Time Point)	Primary vs. Supportive Approach †	Statistical Method	Analysis Population	Missing Data Approach
Primary Endpoints				
IgG response rates at 30 days PD3	P	Descriptive Statistics (estimate, 95% CI)	PP	Missing data will not be imputed
	S		FAS	
IgG GMCs at 30 days PD3	P	Descriptive Statistics (estimate, 95% CI)	PP	Missing data will not be imputed
	S		FAS	
Secondary Endpoint				
IgG GMCs at 30 days PD4	P	Descriptive Statistics (estimate, 95% CI)	PP	Missing data will not be imputed

† P=Primary approach; S=Supportive approach.  
CI = confidence interval; FAS = Full Analysis Set; GMC = geometric mean concentration;  
IgG = immunoglobulin G; PP = Per-Protocol.

### 9.6.2 Statistical Methods for Safety Analyses

Safety and tolerability will be assessed by clinical review of all relevant parameters including AEs and postvaccination temperature measurements.

The analysis strategy of safety parameters is summarized in [Table 4](#). The proportion of participants with solicited injection-site AEs (swelling, redness/erythema, tenderness/pain, and hard lump/induration from Day 1 to Day 7 postvaccination) and solicited systemic AEs (irritability, drowsiness/somnolence, hives or welts/urticaria, and appetite loss/decreased appetite from Day 1 to Day 7 postvaccination) will be provided along with the corresponding CIs (based on the exact binomial method proposed by Clopper and Pearson [CLOPPER, C. J. and PEARSON, E. S. 1934]). In addition, the broad AE categories consisting of the proportion of participants with any AE, a vaccine-related AE, an SAE, a vaccine-related SAE, discontinuation due to an AE, and the proportion of participants who died will be summarized in the same manner. The proportion of participants with maximum temperature measurements meeting the Brighton Collaboration cut points (from Day 1 through Day 7) [Marcy, S. M., et al 2004] will also be provided along with the corresponding 95% CIs. Point estimates will be provided for all other safety parameters (specific AE terms and system organ class terms).

Medical device incidents due to syringe, if any, will be listed.

The safety parameters may be summarized separately as soon as complete data become available at 30 days after the third dose of V114 and 30 days after the fourth dose of V114.

Table 4 Analysis Strategy for Safety Parameters

Safety Endpoint	95% CI	Descriptive Statistics
Injection-site redness/erythema (Day 1 to Day 7) †	X	X
Injection-site swelling (Days 1 to 7) †	X	X
Injection-site tenderness/pain (Days 1 to 7) †	X	X
Injection-site hard lump/induration (Days 1 to 7) †	X	X
Irritability (Days 1 to 7) †	X	X
Drowsiness/somnolence (Days 1 to 7) †	X	X
Hives or welts/urticaria (Days 1 to 7) †	X	X
Appetite loss/decreased appetite (Days 1 to 7) †	X	X
Any AE ‡	X	X
Any Vaccine-related AE ‡	X	X
Any SAE ‡	X	X
Any Vaccine-related SAE ‡	X	X
Discontinuation due to AE ‡	X	X
Death ‡	X	X
Maximum temperature measurements meeting the Brighton Collaboration cut points (Days 1 to 7)	X	X
Specific AEs by SOC and PT		X

AE = adverse event; CI = confidence interval; PT = preferred term; SAE = serious adverse event; SOC = system organ class; X = results will be provided.

† Includes solicited events only.

‡ These endpoints are broad adverse event categories. For example, descriptive statistics for the safety endpoint of “Any AE” will provide the number and percentage of participants with at least 1 AE.

